5.1.1 Outcome Measures

The primary outcome measure will be the CAPS, a clinician-administered measure for PTSD diagnosis and assessment of symptom intensity and frequency. A qualified, blinded IR will perform the CAPS at baseline and outcome measurement timepoints. The IR will not be present during the subject’s experimental sessions nor have any information regarding the experimental sessions. Subjects will be instructed not to inform the IR of any beliefs they or others have concerning their condition assignment during the evaluation session. The CAPS provides a standardized method to evaluate the frequency and intensity dimensions of each symptom, impact of symptoms on the subject’s social and occupational functioning, overall severity of the symptom complex and global improvement since baseline and the validity of the ratings obtained. The CAPS interview takes approximately one hour to complete. All assessments, including those at baseline, will use the CAPS assessment of symptoms over the last month. The CAPS has been determined to have good internal consistency, concurrent validity, and test/retest reliability [115, 116].

The secondary measure of PTSD symptoms will be the PDS, a self-report measure designed to follow DSM-IV criteria for assessing PTSD. The measure is derived from the Posttraumatic Symptom Scale – Self Report (PSS-SR), a measure also intended to tap into diagnostic criteria for PTSD. The PDS contains 49 items, with responses made on a four-point scale, ranging from 0 (“not at all”) to 3 (“five or more times a week”). The PDS consists of a list of 12 potential traumatic events, 12 items addressing elements of the traumatic event, of 17 symptom items, and nine items assessing impact on areas of life function [117]. Items addressing elements of the traumatic event and life function are answered as either present or not present (Yes or No). The 17 items are summed to create a symptom severity scale. Cronbach’s alpha for the symptom severity scale is 0.92. The PDS has test-retest reliability of 0.74 after a two-week and one-month interval, and subscales are inter-correlated, with correlations ranging from 0.73 to 0.82, and PDS scores have a moderate to good correlation with SCID diagnosis, with kappa = 0.65 [117]. Subjects will complete the PDS questionnaire at baseline, after each experimental session, and the end of Stage 1 or Stage 2, as specified in the Time and Events Table.

The BDI-II is a 1996 revision of the BDI, a 21-item self-report measure [118, 119], that will serve as a measure of depression according to DSM-IV criteria [120]. The BDI-II has been validated, has high internal consistency and good test/re-test reliability and is not overly sensitive to daily variations in mood. It takes five to ten minutes to complete [120]. Score cutoffs indicate: 0-13 minimal depression, 14-19 mild depression, 20-28 moderate depression, and 29-63 severe depression. Higher scores indicate more severe depressive symptoms. Subjects will complete the BDI-II at the same times as the CAPS.

The GAF is a measure of quality of life and general function made through observations. The GAF consists of a single score, with scores ranging from 0 to 100, with 100 reflecting superior function and 0 reflecting serious risk of causing harm to the self or others. The GAF is a reliable, validated measure of social functioning [121]. Subjects will complete the GAF at the same time as the CAPS.

The PSQI is a measure of self-reported sleep quality over a one-month period. The PSQI was designed to be a reliable, standardized measure able to distinguish between good and poor sleepers. It consists of 19 items, with possible responses ranging from 0 to 4 on a five-point scale [122]. The PSQI consists of seven sub-scales; sleep quality, sleep latency, sleep duration, habitual sleep efficiency, sleep disturbance, use of sleeping medications, and daytime dysfunction. These are all summed to produce a single global scale. Global scores can range from 0 to 21, with higher scores reflecting poorer sleep quality, and a score below 5 indicative of good sleep. It takes five to 10 minutes to complete. Test-retest reliability ranges from 0.85 to 0.87, and it is internally consistent, with a Cronbach’s alpha of 0.83 [122, 123]. Global scores correlate with other measures of alertness and self-reported sleep quality [124]. Subjects will complete the PSQI at the same time as the CAPS.

The PTGI is a 21-item self-report measure of perceived growth or benefits occurring after a traumatic event. It contains five subscales; relationship to others, new possibilities, personal strength, spiritual change, and appreciation of life [125, 126]. In this study,

subjects will complete the PTGI in reference to the time since the trauma at baseline, but will respond in reference to the beginning of their participation in the study on all subsequent occasions. Subjects will complete the PTGI according to the Time and Events table.

The DES-II is a 28-item self-report measure of dissociation, defined as a lack of normal integration of an individual's thoughts, feelings, or experiences into the stream of consciousness or memory [127, 128]. It is an established measure of dissociative symptoms. The scale consists of statements describing facets of dissociation. Respondents indicate how often the specific experience happens to them, from "never" to "always." Responses on the original scale were made via visual analog scales. The DES-II uses the same items but with responses made on a ten-point scale from "0%" to "100%" of the time. The scale is scored by treating percentages as single digits to produce a total score. The DES-II can also be used to produce scores for three factors, amnesia, depersonalization, and derealization. The scale differentiated between respondents without psychiatric disorders or with psychiatric disorders with few dissociative symptoms and respondents with psychiatric disorders associated with dissociative symptoms [127]. Reliability of the DES-II is high (ranging from 0.79 to 0.96 in an early review), and a reported Cronbach's alpha of 0.95 [128, 129]. There may be a relationship between experiencing dissociation and occurrence of chronic PTSD [128, 130].

The long-term follow-up questionnaire has been developed internally by the Sponsor to assess long-term benefits and harms of MDMA-assisted psychotherapy at the long-term follow-up visit.

5.1.2 Safety Measures

Safety measures will be applied as described below to minimize risks associated with drug-assisted psychotherapy sessions. The therapists or study physician will be available via mobile phone or pager throughout the study to ensure subject safety. The therapists will maintain Basic Life Support (BLS) certification.

Safety measures, including vital signs and a measurement of psychological distress, will be assessed during all experimental sessions. Subjects will rate their current degree of subjective distress with the SUD scale, which is a single-item self-report scale. The SUD will be completed repeatedly during the experimental sessions, with the degree of distress marked along seven points. Results of the SUD are intended to assist therapists in maintaining subject safety during experimental sessions.

The therapists will assess general wellbeing during each preparatory session, on each integrative session and during telephone calls for seven days. Results of this scale are intended to assist therapists in maintaining subject safety throughout the study.

The C-SSRS is a clinician-administered measure of suicidal behavior devised to detect potential suicidal thoughts or behaviors during a clinical trial [131]. It consists of a

“Baseline” form that assesses lifetime suicidal ideation, ideation intensity, and behavior and a form for assessing current suicidal ideation and behavior. The C-SSRS consists of a series of questions, and can be administered during a face-to-face interview or over the telephone. Suicidality will be assessed at baseline, during most face-to-face visits, during the second and seventh days of telephone contact, and twice during each experimental session. Subjects who are discontinuing medication to participate in the study will complete the C-SSRS before and after medication washout. The C-SSRS data will be collected on Case Report Forms (CRFs) for all administrations except for the second integrative session, unless the therapists observe an increase in suicidality. C-SSRS data from the second integrative session after each experimental session will be kept with the subject’s source record.

The Repeatable Battery for the Assessment of Neuropsychological Status (RBANS) [132] is a relatively brief battery of assessments for cognitive function. It consists of 12 subtests that cover verbal and visual memory and attention and takes approximately 30 minutes to administer. Tasks include recall of lists, figures and stories, picture naming, semantic fluency, copying a figure, digit span and coding, and line orientation. Scores on the RBANS subtests can be used to obtain a total score and five index scores; attention, immediate memory, delayed memory, language and visuospatial/constructional scores. Factor analyses of the RBANS and samples of veterans and people with schizophrenia suggest that the RBANS possesses two factors rather than five [133, 134]. The RBANS has alternate forms, allowing repeated administration. Test performance by healthy controls were distinguishable from performance by people with probable Alzheimer’s disease or the neurodegenerative condition Huntington’s disease [135], and the test has high split-half reliability, with coefficients ranging from 0.80 to 0.88 [132]. Test-retest reliability is good for total RBANS scores in healthy controls and psychiatric patients [136]. The RBANS has been used in community-based and psychiatric samples [133, 137] and in a prospective investigation of the effects of chemotherapy upon cognitive function [138]. Each administration of the RBANS will use one of parallel forms of RBANS, and each participant will not complete the same form twice. This measure was employed as a means of assessing safety after two sessions of MDMA-assisted psychotherapy for PTSD [1]. See Time and Events Table for a detailed schedule.

The Paced Auditory Serial Addition Test (PASAT) is a measure of psychomotor speed, auditory information processing and computation ability [139]. The PASAT was originally designed to assess recovery after traumatic brain injury, and has been used subsequently to assess cognitive function in other populations [139-141]. It takes approximately ten to 15 minutes to administer. The measure involves the addition of a series of digits presented at a three or two second interval, with responses made by adding each number to the prior digit. The PASAT consists of two alternate forms, permitting repeated administration. PASAT scoring includes collecting number of correct and incorrect responses, time to response (latency of response) and any failure to respond. There was a positive correlation between responses on the PASAT and a non-numerical paced measure. The measure is internally consistent (Cronbach’s alpha of 0.90), and it has high test-retest reliability, with reliability ranging from 0.90 to 0.97 [140-142]. The first administration of the PASAT will use one of the two alternate forms,

and the second administration will use the other. This measure was employed as a means of assessing safety after two sessions of MDMA-assisted psychotherapy for PTSD [1]. See Time and Events Table for a detailed schedule.

Cardiovascular effects will be assessed via blood pressure and pulse measurement. Blood pressure and heart rate will be assessed periodically during each experimental session by an automatic blood pressure (BP) and pulse monitor. Blood pressure and pulse will be measured at the outset of the experimental session, and once approximately every 30 minutes for the first four hours of the experimental session, and once every hour, or as needed, thereafter. More frequent measures will be taken if the established thresholds of 160 systolic, 110 diastolic, or pulse of 110 are exceeded. Blood pressure will also be measured more frequently if there are symptoms, such as chest pain, shortness of breath or neurological symptoms that may be indicative of hypertension. The therapists will measure subject body temperature approximately every 60 to 90 minutes. Cardiovascular effects will be assessed via blood pressure measurement. The timing of these measurements will be adjusted so they do not interfere with the therapeutic process.

A 100-millimeter visual analog scale will be used to assess changes in symptoms of pre-existing tinnitus and/or chronic pain [143-145]. The Changes in Tinnitus and/or Pain visual analog scale will allow rating of symptom severity from “None” to “Worst Case Imaginable”. This exploratory measure will enable quantification of subjective somatic symptoms that are known to be associated with PTSD [144, 146-148]. Presence of chronic pain is associated with PTSD, possibly as a result of psychological response to traumatic stress as reflected in brain activity, such as increased amygdalar activity in response to pain and transmitter systems involved in the stress response [144, 147, 148].

All AEs and spontaneously reported reactions will be collected, as described in Section 8.5. AEs and spontaneously reported reactions may be collected during face-to-face visits or over the telephone. Common reactions that are spontaneously reported are collected for seven days after each experimental session on a separate CRF page and will be categorized as mild, moderate, or severe.

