Overnight Stay, SOCQ			✓		✓			✓		
Integrative Therapy Session				✓ ^A		✓ ^A			✓ ^A	
Seven Days Telephone Contact				✓		✓			✓	
AEs Requiring Medical Attention		✓	✓	✓	✓	✓	✓	✓	✓	✓
Spont. Reported Reactions & all AEs			✓ ^J	✓	✓ ^J	✓	✓	✓ ^J	✓	
Changes in Tinnitus and/or Pain	✓ ^P		✓ ^{E,P}	✓ ^{E,P}	✓ ^{E,P}	✓ ^{E,P}	✓ ^P	✓ ^{E,P}	✓ ^{E,P}	✓ ^P
AEs of psychiatric status or withdrawal		✓	✓	✓	✓	✓	✓	✓	✓	✓
Serious Adverse Events		✓	✓	✓	✓	✓	✓	✓	✓	✓
Issue Memory Aid Card										✓ ^H
Unblinding							✓			
Perception of Experimental Sessions							✓ ^N			✓ ^N
RRPQ										✓ ^H

A = First Integrative session is one day after experimental session; B = At least 24 hours prior to experimental session; C = Approximately six hours post MDMA; D = At the beginning of the session; E = As needed; F = Approximately every 60 minutes; G = Given on 2nd preparatory session after washout; H = Only for subjects starting long-term follow-up; I = All visits and Day 2 and Day 7 phone calls only; J = Reactions collected for seven days post experimental session; K = On the day of the first integrative session following the experimental session; L = One month after the second experimental session but before the third experimental session; M = On the day of the third integrative session; N = Active dose subjects only; O = Only on Visit 1; P = Only in subjects with pre-existing tinnitus and/or chronic pain.

Table 3. Time & Events Stage 2		Preparatory Session	Experimental Session 1		Experimental Session 2		Secondary Endpoint	Experimental Session 3		End of Stage 2	Long-term Follow-up
Visit #	V18*	V19	V20,21,22	V23	V24,25,26	V27	V28	V29, 30, 31	V32		LTFU
Type of Visit	Preparatory	Experimental	Integrative	Experimental	Integrative	Outcome	Experimental	Integrative	Outcome		Follow-up
Visit Timing	Within 1 month post V12*	1 week post V18	Between V19 and V23	3-5 weeks post V19	Between V23 and V27	1 month post V23	1 month post V23	Between V28 and V32	2 months post V28		1 year post V13 or V28
Confirm Informed Consent	✓										
Confirm Inclusion/Exclusion	✓										
Enrollment in Stage 2	✓										
Collect Concomitant Medication	✓	✓	✓	✓	✓	✓	✓	✓	✓		✓
Record to Audio/Video	✓	✓	✓	✓	✓		✓	✓			
General Well-Being	✓	✓	✓	✓	✓	✓	✓	✓			
Drug Screen		✓		✓			✓				
Pregnancy Screen (if applicable)		✓		✓			✓				
CAPS, GAF, BDI-II, PSQ, PTGI, DES-II	Use V12*					✓ ^H			✓		✓
RBANS/PASAT									✓		
PDS	Use V12*		✓ ^I			✓		✓ ^I	✓		✓
C-SSRS	✓	✓ ^{B,C,D}	✓ ^G	✓ ^{B,C,D}	✓ ^G	✓	✓ ^{B,C,D}	✓ ^G	✓		✓

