- a. Record each integrative session to audio and video. Subjects will be given access to review one or more integrative sessions upon request.
- b. The C-SSRS will be administered just prior to beginning each integrative session.
- c. General wellbeing will be assessed at each integrative session.
- d. If subjects who have pre-existing tinnitus or chronic pain mention any changes, use the visual analog scale to collect the changes in symptoms.
- e. The subject will complete the PDS questionnaire after each experimental session on the third integrative session or primary endpoint (after the second experimental session only), according to the Time and Events Table.
- f. The subject and therapists will continue to work on supporting the subject as she or he considers his or her experiences during experimental sessions.
- g. The therapists will use clinical judgment to assess the subject's psychological wellbeing during this period of time. If there are any indications of continuing anxiety or distress, the therapists may arrange to work on reducing the distress at a specially scheduled integrative therapy session, through continuing contact, or at the next regularly scheduled integrative therapy session. The subject may also initiate contact with the therapists at any time throughout the study.
- h. Collect AEs and medications, as described in Sections 8.5 and 9.0.
- i. NOTE: If an integrative session falls within the period of telephone contact and additional phone call is not required that day, all data normally collected during the telephone call will be completed in person.

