9.5 Baseline Values

Baseline values are from screening/baseline visit for all measures, except C-SSRS. For C-SSRS, pre-enrollment scores will be used as a measure of ‘lifetime’ suicidal ideation and behavior, and preparatory session 2 (visit 2) prior to drug administration will be used as ‘baseline.’ If a subject was not administered the C-SSRS at preparatory session 2 (visit 3), then ‘baseline’ scores will be visit 4 pre-drug C-SSRS observation.

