9.9.4 Safety Analyses

The primary measure of safety will be the reporting of adverse events. The Adverse events considered are Treatment Emergent Adverse Events (TEAE) defined as those AE's that occurred after dosing and existing medical history diagnoses that worsened during the study. Verbatim terms on case report forms will be mapped to preferred terms and system organ classes using the MedDRA dictionary. For incidence reporting if a subject has more than one AE mapped to the same preferred term, that AE will be reported only once using the highest severity and closest relationship to study drug. Subject incidence of AEs will be displayed by Stage I treatment group and by system organ class. AEs will also be summarized by severity and relationship to study drug. Subject incidence of SAEs by Stage I treatment group will also be displayed. In addition to the listing of all AEs, a listing of SAEs and a listing of AEs leading to discontinuation of study drug will be included.

Summary tables of frequency listings of commonly reported AEs (Spontaneously Reported Reactions) mapped to preferred terms will be displayed during and after each experimental session by Stage 1 treatment group.

Columbia Suicide Severity Rating Scale (C-SSRS)

Suicidal ideation and behavior will be summarized according to suggestions made in the Columbia-Suicide Severity Rating Scale Scoring and Data Analysis Guide [2]. A positive response for suicidal ideation is counted when a subject answers "yes" to any one of the five suicidal ideation questions (Categories 1-5) on the C-SSRS, i.e. a score > 0 for suicidal ideation score. Serious suicidal ideation is a suicidal ideation score of 4 or 5. A positive response for suicidal behavior occurs when a subject answers "yes" to any one of the five suicidal behavior questions (Categories 6-10) on the C-SSRS, i.e. a score > 0 for suicidal behavior score. The number and percent of positive responses of Positive Ideation, Serious Ideation, and Positive Behavior will be tabulated by Stage I treatment group and time period. Compare lifetime serious suicidal ideation and positive behavior frequencies to cumulative frequencies anytime during the study until end of Stage 1 and Stage2.

Subjective Units of Distress (SUD)

Descriptive statistics for SUD scores will be calculated by Stage 1 treatment group and time period with counts and percentages.

Visual analog scale for Tinnitus and/or Pain visual analog scale

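### C-SSRS data from the second integrative session are entered on the CRF only if an undefined increase is seen; separately, the one named before-after comparison of suicidality uses lifetime history, not the pre-drug baseline

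*Protocol*

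**What the plan says.** **Administration.** Protocol 5.1.2 states: "Suicidality will be assessed at baseline, during most face-to-face visits, during the second and seventh days of telephone contact, and twice during each experimental session". Protocol 5.2.6 adds: "The C-SSRS will be administered just prior to beginning each integrative session", and 5.2.4 requires the scale at the integrative session on the morning after dosing. The Stage 1 schedule footnote reads "I = All visits and Day 2 and Day 7 phone calls only", and Stage 2 has the same rule.

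**Capture.** Protocol 5.1.2 enters C-SSRS data on the CRF "for all administrations except for the second integrative session, unless the therapists observe an increase in suicidality". It continues: "C-SSRS data from the second integrative session after each experimental session will be kept with the" subject's source record. The visits concerned are V6, V10 and V15 in Stage 1, and V21, V25 and V30 in Stage 2. Nothing says what an increase is measured against.

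**Analysis.** SAP 9.9.4 tabulates the number and percent of subjects with any ideation, serious ideation (score 4 or 5) and any behavior, by Stage 1 group and time period. It then gives one before-after instruction: "Compare lifetime serious suicidal ideation and positive behavior frequencies to cumulative frequencies anytime during the study until end of Stage 1 and Stage2".

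**Baseline.** SAP 9.5 keeps lifetime history separate from a pre-treatment value: the form from preparatory session 2 "prior to drug administration will be used as ‘baseline". SAP 9.9.4 does not name that baseline in any comparison.

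**The concern.** There are two separate problems.

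1. At the second integrative session the scale is completed, but its result decides whether it reaches the database. The decision belongs to the treating therapists and has no stated threshold. A percentage calculated from such data has no clear meaning.

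2. The named before-after comparison sets a lifetime look-back against a few months. Protocol exclusion 10 keeps out people at serious current suicide risk but not people with a past history. A lower on-study figure can therefore arise with no treatment effect, or despite an adverse one.

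Suicidality is a named safety objective (Protocol 3.3, SAP 4.3), most subjects' psychiatric medication must be stopped, and the data are to be combined with other Phase 2 studies. A flawed summary would be carried forward.

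**Working it through.** The documents give no C-SSRS rate, so there is no stated figure to reproduce. The counts below come from the schedule. All rates are assumptions.

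**A. How many forms are affected.** Each session cycle has 7 scheduled administrations: pre-dose, about 6 hours, three integrative sessions, and the Day 2 and Day 7 calls. Six are post-dose, and one of those is conditional.

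- Up to V12: screening 1 + preparatory 1 + 2×7 + V12 1 = 17, of which 2 are conditional.
- Up to V17: 2 + 3×7 + 2 = 25, of which 3 are conditional.
- Stage 2: 1 + 3×7 + 2 = 24, of which 3 are conditional.
- All cycles at 12:9:5, everything completed: 12×3 + 9×3 + 5×2 + 5×3 = 88.
- Blinded sessions: 26×2 = 52. Open-label sessions: 21 + 15 = 36.
- At the protocol's 9:9:5: 18×3 + 5×5 = 79.

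The 88 is a ceiling for the 26 planned subjects, since forms showing an increase are entered. The two early withdrawals described in SAP 9.3 could add at most one form each.

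**B. Effect at the visit and on the cumulative figure.** If only recorded forms are counted, each comes from a subject judged to have increased, so the percentage with any ideation is near 100%. If blanks count as negative, unchanged positives are lost. I simulated seven assessments per session in 200,000 subjects. Each kept the previous state with probability 0.6 and otherwise redrew it at prevalence p. Lifetime history was set at 50%, plus anyone positive pre-dose. A positive was recorded at the second integrative session only if the reference was negative.

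| True % at visit | Recorded, vs previous form | vs pre-session form | vs lifetime | Cumulative true | Cumulative captured |
|---|---|---|---|---|---|
| 5 | 1.9 | 4.1 | 2.1 | 15.7 | 15.4 to 15.7 |
| 10 | 3.6 | 7.8 | 3.9 | 29.4 | 28.9 to 29.4 |
| 20 | 6.5 | 13.8 | 6.9 | 51.3 | 50.6 to 51.3 |

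The visit figure loses between about a fifth and two thirds of positives, depending on what an increase means. The cumulative figure barely moves, because a positive that is not an increase over an earlier on-study form was already positive on a form that is entered. This holds if the reference form itself counts in the cumulative figure. A count starting strictly after the first dose could lose a little more.

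**C. Length of the on-study look-back.**

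- Active groups, V4 to V17: about 1 + 1 + 2 = 4 months, if session 3 follows V12 promptly.
- Crossover subjects, V4 to V32: about 1 (to V8) + 1 (to V12) + up to 1 (to V18) + 0.25 (to V19) + 1 (to V23) + 1 (to V28) + 2 (to V32), or about 7 months.

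**D. What the lifetime contrast can show.** Take n = 26, with L subjects positive over their lifetime, b at the pre-drug baseline and s on study. The lifetime contrast is 100(s − L)/26 and the baseline contrast is 100(s − b)/26, in percentage points.

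| Lifetime L | b=2, s=4 (baseline contrast +8) | b=2, s=6 (+15) | b=4, s=8 (+15) |
|---|---|---|---|
| 6/26 | −8 | 0 | +8 |
| 10/26 | −23 | −15 | −8 |
| 14/26 | −38 | −31 | −23 |
| 18/26 | −54 | −46 | −38 |

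Suicidality rises from baseline in all 12 cases. The lifetime contrast shows a fall in 10, no change in one and a rise in one.

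**E. Dependence on the lifetime rate.** With monthly risk m, multiplier k and four months, on-study incidence is 1 − (1 − mk)^4. For m = 0.01 to 0.05 this gives 4% to 19% at k = 1 and 12% to 48% at k = 3, all below an assumed lifetime rate of 50% to 60%. At a lifetime rate of 30%, m = 0.03 and k = 3 give 1 − 0.91^4 = 31%, which is above lifetime.

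**The case against.** The strongest reply is that neither problem leaves the trial without a usable suicidality display. SAP 9.9.4 tabulates by Stage 1 group and time period before it mentions lifetime history. Protocol 3.3 and SAP 4.3 call for comparisons between groups, and the lifetime line carries no test. This stands: lifetime history is not the only yardstick, and a dose-related rise could appear in the randomised tables.

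Several stronger readings are tempting and fail:

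- A reader might infer that the capture rule makes worsening look like improvement. It does not. Increases are exactly what it sends to the CRF, and the cumulative figure hardly changes.
- A reader might infer that on-study rates must fall below lifetime. Part E shows that this depends on an assumed lifetime rate, and exclusion 10 could lower the real one.
- A reader might infer that therapists judge the increase knowing the dose. After V12 they do by design (36 of the 88 forms). For the blinded sessions, Protocol 5.1.3 collects beliefs about assignment but the documents report no results.

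Other mitigation is real but partial. The forms remain in source, and psychiatric adverse events are collected throughout (Protocol 8.5), though these do not supply C-SSRS scores. SAP 9.3 bases safety analyses on all enrolled subjects with available data, which does not settle how a blank form is counted. SAP 9.9.4 also cites a scoring guide that cannot be consulted here. If it defines worsening, the SAP should name that definition.

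**Conclusion.** Both points hold, separately and within limits.

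1. **Capture.** Second-integrative-session C-SSRS data are missing according to their own value: 1 of 6 post-dose administrations per cycle, at most 88 forms, at most 52 of them blinded. That visit's by-period percentage is uninterpretable under either denominator. If time periods pool several visits, the distortion is diluted. The cumulative frequency is close to right.

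2. **Comparator.** The only named before-after comparison has look-backs so unequal that it can show a fall while suicidality rises from the pre-drug baseline. The direction is not guaranteed, and its frequency rests on rates the documents do not give.

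The counts rest on the schedule and full completion; the percentages rest on the stated assumptions. The gap is in data capture and analysis, not in administration of the scale. Both should be corrected, because each changes a reported safety result.

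**What to change.** - **Protocol 5.1.2:** delete the exception so that every C-SSRS administration is entered on the CRF, and back-enter completed second-integrative-session forms from source.
- **SAP 9.9.4:** by Stage 1 dose group, report the number of subjects whose post-dose ideation score exceeds their own pre-drug baseline, and the number with new serious ideation (4 or 5) or behavior. Such counts grow with the number of assessments, so the informative contrast is between dose groups over the same window, such as up to V12. State the denominator for each period. Keep lifetime history as descriptive context only.
- **SAP 9.5:** preparatory session 2 is called visit 2 in one sentence and visit 3 in the next. Reconcile them, since the new comparison depends on that baseline.

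The cost is entry of at most 88 existing forms (79 at 9:9:5), plus up to two from the early withdrawals, and a few SAP sentences. No new visits, assessments or staff are needed.
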